10.5 Analysis of secondary objectives

10.5.1 Efficacy (secondary)

Objective response rate (ORR) is defined as the proportion of patients in whom a complete (CR) or partial (PR) response was observed at week 12 according to RECIST. Absolute and relative frequencies of patients in whom an objective response (CR/PR) was observed at week 12 will be presented together with the 95% confidence interval for the ITT and PP population.

Duration of response is defined as the time from onset of response (CR/PR) to progression or death from any cause. Patients, not experiencing progression or death at 16 weeks will be censored with the date of their last assessment. Duration of response will be explored graphically by presenting the Kaplan-Meier curve.

Progression-free survival (PFS) is defined as the time from first study drug administration to objective tumor progression or death from any cause. Observations from patients not experiencing tumor progression or death at 16 weeks will be censored with the date of their last assessment. PFS will be explored graphically by presenting the Kaplan-Meier curve. Additionally, the Kaplan-Meier curve will be presented for PFS at 12 months.

Overall survival (OS) is defined as the time from first study drug administration to death from any cause. Patients, not experiencing death at 16 weeks will be censored with the date of their last assessment. OS will be explored graphically by presenting the Kaplan-Meier curve.

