Clinical Development

RAD001

CRAD001C24114 / NCT00767819

Multicenter, triple-arm, single-stage, phase II trial to determine the preliminary efficacy and safety of RAD001 in patients with histological evidence of progressive or metastatic bone or soft tissue sarcomas

RAP Module 3 – Detailed statistical methodology

Author:

[REDACTED]

Document type: RAP Documentation

Document status: Final 1.0

Release date: 07-Jul-2011

Property of Novartis
Confidential

May not be used, divulged, published or otherwise disclosed
without the consent of Novartis

Novartis approval signatures for:

RAP Module 3 – Detailed statistical methodology

Signature

Date

Signature

Date

1 Data analysis

This was a non-randomized, multicenter, triple-arm, phase II trial evaluating the treatment of RAD001 in the following three arms: in patients with progressive or metastatic bone or soft tissue sarcoma (except for GIST), in patients with progressive or metastatic GIST after failure or intolerance of treatment with imatinib or sunitinib, and in patients with progressive or metastatic alveolar soft part sarcoma (ASPS), respectively.

The study was designed to assess the activity, safety, and tolerability of the therapy with RAD001 in progressive bone or soft tissue sarcoma in the **three** arms each.

The data were analyzed by Novartis. Any data analysis carried out independently by the investigator(s) was recommended to be submitted to Novartis before publication or presentation. It was planned that the data from participating centers in this protocol were combined within each of the arms, so that an adequate number of patients was available for analysis.

Data were summarized with respect to demographic and baseline characteristics, efficacy observations and measurements, safety observations and measurements, and pharmacokinetic measurements. Categorical data were presented as absolute frequencies and percentages. For continuous data, N (the number of valid observations), N miss. (the number of missing observations), mean, standard deviation, median, minimum, and maximum were presented.

It was planned that the data of each arm were to be analyzed and reported independently of the other arm once the number of patients needed for analysis was reached. However, the methods described in this analysis plan apply for all three arms, if not otherwise indicated.

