1.4 Analysis of the primary objective(s)

1.4.1 Variable

The primary variable is defined as the proportion of patients in whom a best overall response of complete (CR) or partial (PR) response or stable disease (SD) was observed at 16 weeks according to RECIST (version 1.0, [Therasse et al. 2000](#)) based on local radiologic assessments.

The best overall response for each patient was determined from the sequence of overall (lesion) responses at Visit 4/Week 8 and Visit 6/Week 16, respectively, according to the following rules (see Post-text supplement 1 to the study protocol):

- CR = at least two determinations of CR at least 4 weeks apart before progression.
- PR = at least two determinations of PR or better at least 4 weeks apart before progression (and not qualifying for a CR).
- SD = at least one SD assessment > 6 weeks after start of treatment (and not qualifying for CR or PR).
- PD = progression or death due to underlying cancer ≤ 16 weeks after start of treatment (and not qualifying for CR, PR or SD). Patients with symptoms of rapidly progressing disease without radiologic evidence will be classified as progression only when clear evidence of clinical deterioration is available and patient discontinued due to 'Disease progression'. Furthermore, patients without radiologic evidence for progression who were prematurely discontinuing from the study for 'unsatisfactory therapeutic effect', 'new cancer therapy' or 'death' (from any reason) will be classified as progression.
- UNK = all other cases (i.e. not qualifying for confirmed CR or PR and without SD after more than 6 weeks or early progression within the first 16 weeks)

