1.5 Analysis of secondary objectives

1.5.1 Efficacy (secondary)

Secondary efficacy variables were analyzed for the ITT set.

Objective response rate (ORR) was defined as the proportion of patients in whom a complete (CR) or partial (PR) response was observed at Visit 6/Week 16 according to RECIST (version 1.0) based on central radiologic review. Absolute and relative frequencies were presented together with the appropriate exact confidence interval.

Duration of stable disease (CR, PR or SD) applied only to those patients whose best overall response was CR, PR or SD based on local radiologic assessments and was defined as the time from start of treatment to progression or death from underlying disease. Patients not experiencing progression or death at 16 weeks were censored with the date of their last tumor assessment. Duration of response was explored using the Kaplan-Meier method. The Kaplan-Meier estimate for median duration of response as well as the Kaplan-Meier curve was displayed. Although duration of response (CR or PR) was planned to be analyzed within the protocol, this was changed to reach a more valuable analysis since no patient reached a best overall response of CR or PR.

Progression-free survival (PFS) was defined as the time from the date of start of treatment to the date of event defined as the first documented progression or death from any cause. If a patient had not had an event, PFS was censored at the date of the last adequate tumor assessment, which was the date of Visit 6 for the core study phase and the last available tumor assessment for the follow-up phase. PFS was explored by using the Kaplan-Meier method. The Kaplan-Meier estimate for median PFS as well as the Kaplan-Meier curve was displayed.

Time to progression (TTP) was defined as the time from the date of start of treatment to the date of event defined as the first documented progression or death from underlying disease. If a patient had not had an event, TTP was censored at the date of the last adequate tumor assessment, which was the date of Visit 6 for the core phase and the last available tumor

assessment for the follow-up phase. TTP was explored by using the Kaplan-Meier method. The Kaplan-Meier estimate for median TTP as well as the Kaplan-Meier curve was displayed.

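### The SAP's substitute for duration of response counts from treatment start in patients selected for being event-free past 6 weeks, narrows the death event without explanation, and keeps the response label

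*SAP*

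**What the plan says.** Protocol 10.5.1: "Duration of response is defined as the time from onset of response (CR/PR) to progression or death from any cause". Its censoring rule follows: "Patients, not experiencing progression or death at 16 weeks will be censored with the date of their last assessment".

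SAP 1.5.1 replaces this with a duration of stable disease. It "applied only to those patients whose best overall response was CR, PR or SD based on local radiologic assessments" and is "defined as the time from start of treatment to progression or death from underlying disease". Censoring reads: "Patients not experiencing progression or death at 16 weeks were censored with the date of their last tumor assessment". The reason given is that "this was changed to reach a more valuable analysis since no patient reached a best overall response of CR or PR". The same paragraph then describes the Kaplan-Meier median and curve as showing duration of response.

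Who enters the set depends on SAP 1.4.1: "SD = at least one SD assessment > 6 weeks after start of treatment (and not qualifying for CR or PR". That section derives best response from the week 8 and week 16 visits.

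Two other places matter:

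- The numbered list of changes from the protocol in SAP section 1 has two entries: local instead of central reading, and ITT instead of per-protocol. Duration of response is in neither.
- PFS in SAP 1.5.1 covers the ITT set, counts death from any cause, and runs to the last available tumor assessment in follow-up. TTP also uses follow-up scans, but counts only disease deaths.

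**The concern.** Selection and clock do not match. A patient enters the set by being stable beyond 6 weeks, yet the time before that is credited as duration. The protocol's variable avoided this by starting at the onset of response. The credited weeks say nothing about how long disease control lasts once it is established, and they appear whether or not the drug works.

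The event was also narrowed. A patient with stable disease at week 8 who then dies of toxicity was a failure under the protocol's event definition and is not one under the SAP's. The SAP explains the move from CR/PR to CR/PR/SD, but not this.

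The trial has no control arm, so nothing in the results would reveal the built-in period. A median labelled as duration of response, near 16 weeks or not reached, could be read as drug effect when there were no responders.

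**Working it through.** **The plan's own figures.** The duration variable has none. The nearest are the design figures in Protocol 10.6 and SAP 1.6, which supply the 20% benchmark for an inactive drug. Exact binomial tails reproduce them: n = 36 with at least 11 responders gives a type I error of 0.0889 and a type II error of 0.0904; n = 24 with at least 8 gives 0.0892 and 0.1919. The plan states 8.9%, 9.0%, 8.9% and 19.2%.

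**Inputs.** Scans at weeks 8 and 16 (SAP 1.4.1); selection on being stable at week 8; P0 = 20%. The exponential shape is an assumption, as the documents give no curve.

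**Reading A: 20% are progression-free at 16 weeks.** Both documents say P0 and P1 come from a publication on PFS.

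- Rate: λ = −ln(0.20)/16 = 0.1006 per week.
- ITT PFS median: ln(2)/λ = 6.9 weeks.
- Stable at week 8: exp(−8λ) = 0.447, about 16 of 36 or 11 of 24.
- Of those, progressing by week 16: 1 − 0.20/0.447 = 0.553.
- Median counted from treatment start in the selected patients: 8 + 6.9 = 14.9 weeks.
- On the scan schedule: 55.3% of all patients have progressed at the week 8 scan, so the ITT median is 8; 55.3% of the selected have progressed at the week 16 scan, so their median is 16.

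**Reading B: 20% are stable at week 8.** This matches the SAP's own rule, under which one qualifying SD assessment makes a responder. Under reading A, 44.7% would be responders by that rule, which is above P1 = 40%.

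- λ = −ln(0.20)/8 = 0.2012 per week; ITT median 3.45 weeks.
- Selected median: 8 + 3.45 = 11.45 weeks.
- On the scan schedule: 80% of all patients progress by week 8, and 80% of the selected by week 16, so again 8 against 16.

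Under any exponential the excess is exactly 8 weeks, which is the selection time itself.

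| Assumption | Selected, from start (weeks) | All ITT (weeks) |
|---|---|---|
| 10% progression-free at 16 weeks | 12.8 | 4.8 |
| 20% progression-free at 16 weeks | 14.9 | 6.9 |
| 30% progression-free at 16 weeks | 17.2, past the cut, so not reached | 9.2 |
| 20% stable at week 8 | 11.45 | 3.45 |

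**Sampling variation, reading A.** In 4,000 simulated trials per setting on the scan schedule, the selected-patient median was not reached in about 28% (n = 36) to 32% (n = 24). For ITT PFS the figure was 0%.

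**Deaths from other causes.** The documents give no share. If 10% of the event hazard is non-cancer death, censored at the last scan, not reached rises to about 36% to 38%, a gain of roughly 6 to 9 percentage points.

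**The case against.** The case for leaving the variable alone is substantial. With no responders the planned variable could not be estimated, so no unfavourable result was replaced. SAP 1.5.1 names the planned variable, says it was changed and says why. ITT PFS with any-cause death stands in the same section, with median and curve, and a toxic death remains an event there and in OS. TTP uses the same narrowed event. The censoring sentence mentions death without a cause, and SAP 1.4.1 counts premature discontinuation for death of any cause as progression, so exclusion of non-cancer deaths is not even consistent. No test or power claim attaches to the variable.

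All of this stands and limits the weight of the point. It does not remove the built-in period, explain the event change, or justify the label. The inconsistency over deaths is itself a reason to fix the definition.

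Four stronger readings are tempting but not supported:

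- *The 16-week cut was introduced with the substitute and lengthens the median.* The cut is already in Protocol 10.5.1. It caps the median or leaves it not reached; the lengthening comes from selection combined with the early start. The fair complaint is that it sets aside scans that PFS and TTP use.
- *The median can only be 16 weeks or not reached.* Protocol 7.4 allows unscheduled scans, early discontinuation triggers a tumor measurement, and deaths carry their own dates, so events can fall between the two visits.
- *The variable was chosen because its result looked good.* The SAP, marked "Release date: 07-Jul-2011", shows only that the absence of CR and PR was known. It does not name the arm, and Amendment 7 reports one patient in each of arms II and III still on drug in July 2013.
- *The median reflects no drug effect at all.* Under the same model it moves from 16 weeks at 20% progression-free to not reached at 40%. It is offset by the selection time, not uninformative.

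**Conclusion.** The point holds as one of definition, disclosure and labelling. The guaranteed event-free period of more than 6 weeks follows from the SAP's wording alone. Its size does not: the result of about twice the ITT PFS median (reading A), or about three times (reading B), rests on an exponential curve and on selection at the nominal week 8 visit. The reading of P0 is unsettled, so both should be shown. The direction is the same across the range examined.

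The narrowed death event is a real, unexplained departure from the protocol, with a modest effect within 16 weeks if non-cancer deaths are few. A reader might infer that the activity conclusion is compromised. It is not: that decision counts patients with CR, PR or SD and does not use this duration.

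**What to change.** - Report the planned duration of response as not estimable (0 responders).
- Rename the substitute *duration of disease control, post hoc*, and stop calling its output a duration of response.
- Count death from any cause, as the protocol does, and align the event and censoring sentences.
- Use all follow-up tumor assessments instead of censoring at 16 weeks, as PFS and TTP already do.
- State that included patients are selected for being event-free past 6 weeks, and interpret the result only alongside the planned ITT PFS. Counting from a week 8 landmark is optional.
- Add the substitution and the event change to the list in SAP section 1.

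The cost is SAP wording and one re-run. The description becomes less favourable, since the selection is stated and toxic deaths count. The follow-up scans may in turn give an estimate where the cut would have left the median not reached.

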****This list of clinically relevant drug interactions is updated as of December 02, 2009****

6.3.6 Study drug discontinuation

Study drug must be discontinued for a given patient if the investigator determines that continuing it would result in a significant safety risk for that patient. Patients who, in the opinion of the investigator, require alternative medical therapy, will be discontinued from the study. Patients with a progression will be discontinued from the study. Patients who become pregnant during the study must be withdrawn. If the treatment has to be interrupted for more than 21 consecutive days for any reason, the patient will be discontinued from the study unless otherwise discussed with the study coordinator. In case of patient's discontinuation, the end of study evaluation will be completed as soon as possible. End of study evaluations will include adverse events, concomitant medications and therapies, physical examination, vital signs, ECOG performance status, biochemistry, hematology and tumor measurement.

Patients who discontinue prematurely due to significant AE should continue to be followed-up until resolution of the AE, and the relevant sections of the CRF should be completed as appropriate. Patients who are discontinued due to clinically significant abnormalities in clinical laboratory results should continue to be evaluated until the abnormality resolves or is judged to be permanent.

It will be documented whether or not each patient completed the clinical study. If, for any patient, the study treatment was discontinued the reason will be recorded. Reasons that a patient may discontinue participation in a clinical study are considered to constitute one of the following:

1. Adverse event(s)
2. Abnormal laboratory value(s)
3. Abnormal test procedure result(s)
4. Unsatisfactory therapeutic effect
5. Subject's condition no longer requires study treatment

6. Protocol violation which affect the safety of the patient
7. Subject withdraws consent
8. Lost to follow-up
9. Administrative problems
10. Death

Progressive disease is defined as unsatisfactory therapeutic effect.

For patients who are lost to follow-up, the investigator should show “due diligence” by documenting in the source documents steps taken to contact the patient, e.g. dates of telephone calls, registered letters, etc.

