It is agreed that for reasonable cause, either the investigator or Novartis may terminate this study, provided a written notice is submitted at a reasonable time in advance of the intended termination.

A Study Drug Discontinuation form should be completed, giving the date and primary reason for stopping the study drug.

Study treatment will be continued until progression. Patients will be followed until progression.

The overall survival will be documented on the survival information page for all patients except for those who withdrew consent or are lost to follow-up.

7 Visit schedule and assessments

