7.1 Information to be collected on screening failures

Information on screening failures will be kept in the Novartis Screening Failure Log. No CRF has is needed for screening failures.

All data obtained from the assessments listed in Table 1 and described in detail in the subsections below must be supported in the patient’s source documentation. Assessments that generate data for database entry and which are recorded on CRFs are listed using the CRF name. Assessments that are transferred to the database electronically (e.g. laboratory data) are listed by test name.

The final examination (visit 6 respectively EOS) will be performed for all patients included in this trial (i.e. who signed an informed consent form and received study treatment), whether they discontinued study treatment prematurely or completed the study treatment. Patients who discontinue study drug before completing the core study, and those who prematurely withdraw from the core study for any reason, should be scheduled for the End-of-study-visit as soon as possible, at which time all of the assessments listed for the EOS-visit will be performed.

During the follow-up period, the treatment regimen as taken during the study should be maintained. However, changes in the regimen based on each patient’s clinical needs and the investigators’ experience and discretion will be possible at any time. In the Follow-Up-Phase

	Base-line ¹	Core study						Follow-up ¹²				End of FUP
Visit No.	1	2	3	4	5	6	EOS	FUP 1 - X				
Day	-14	1										
Week			4	8	12	16		28	40	52	X	
Tumor evaluation (RECIST) ⁷	x			x		x	x	x	x	x	x	
Study drug administration		x	x	x	x	x		x	x	x	x	
Adverse events ⁸	x	ongoing data capture						ongoing data capture				
Prior medication	x											
Concomitant medication	x	ongoing data capture						ongoing data capture				
Survival-information ¹⁰												x
Comments		ongoing data capture						ongoing data capture				

¹Described in Section 7.2; 7.5.2

²Described in Section 7.5.3

³Described in Section 7.5.4

⁴Described in Section 7.5.5

⁵Described in Section 7.5.7; 8.2

⁶Described in Section 7.5.6

⁷Described in Section 7.4

⁸Described in Section 8.1.1

⁹Chest x-ray only in cases where no CT/MRI thorax is available

¹⁰Survival information for patients who discontinued earlier

¹¹ Baseline assessment can be done between day-14 and day 1 together with visit 2

¹² During the follow up period patients will continue to be followed every 3 months until progression

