7.5 Safety

7.5.1 Adverse events

An adverse event is the appearance or worsening of any undesirable sign, symptom, or medical condition occurring after date of signed informed consent even if the event is not considered to be related to study drug. Study drug includes the investigational drug under evaluation that is given during any phase of the trial. Medical conditions/diseases present before date of signed informed consent are only considered adverse events if they worsen

after date of signed informed consent. Abnormal laboratory values or test results constitute adverse events only if they induce clinical signs or symptoms, are considered clinically significant, or require therapy (e.g. any hematologic abnormality that requires transfusion or cytokine treatment). In addition, abnormal laboratory values that cause study discontinuation or constitutes in and of itself a Serious Adverse Event (SAE) should be recorded on the Adverse Events CRF.

Adverse events will be assessed according to the Common Terminology Criteria for Adverse Events (CTCAE) version 3.0 (<http://ctep.cancer.gov/forms/CTCAEv3.pdf>). If CTCAE grading does not exist for an adverse event, the severity of mild, moderate, severe, and life-threatening, OR grades 1 – 4, will be used. **CTCAE grade 5 (death) will not be used in this study; rather, this information will be collected in the End of Treatment or Survival Information CRF page.** Adverse event monitoring should be continued for at least 4 weeks following the last dose of study drug.

The occurrence of adverse events should be sought by non-directive questioning of the patient at each visit during the study. Adverse events also may be detected when they are volunteered by the patient during or between visits or through physical examination, laboratory test, or other assessments. As far as possible, each adverse event should be evaluated to determine:

1. the severity grade (CTCAE Grade 1 – 4) or mild, moderate, severe, life-threatening if CTCAE grading does not exist for an adverse event,
2. its relationship to the study drug(s) (suspected/not suspected),
3. its duration (start and end dates or if continuing at final exam),
4. action taken (no action taken; study drug dosage adjusted/temporarily interrupted; study drug permanently discontinued due to this adverse event; concomitant medication taken; non-drug therapy given; hospitalization/prolonged hospitalization), and

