Overall survival (OS) was defined as the time from the date of start of treatment to death from any cause. If a patient was not known to have died, OS was censored at the date of the last contact, which was the date of Visit 6 for the core phase and the last available visit for the follow-up phase. OS was explored by using the Kaplan-Meier method. The Kaplan-Meier estimate for median OS as well as the Kaplan-Meier curve was displayed.

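### Overall survival is censored at the last visit although later survival is recorded, and duration of stable disease has no follow-up clause

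*SAP*

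**What the plan says.** **Overall survival.** SAP 1.5.1 measures OS from start of treatment to death from any cause. A patient with no known death is "censored at the date of the last contact, which was the date of Visit 6 for the core phase and the last available visit" once in follow-up. Contact is thus defined by visits.

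The protocol ends visits at progression. Section 6.3.6 says "Patients with a progression will be discontinued from the study". Section 7.1 says that patients who stop early "should be scheduled for the End-of-study-visit as soon as possible". Table 7-1, footnote 12, says "During the follow up period patients will continue to be followed every 3 months until progression".

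Survival data do not stop there. Section 6.3.6 says that "overall survival will be documented on the survival information page for all patients except for those who withdrew consent or are lost to follow-up". Footnote 10 to Table 7-1 assigns survival information to patients who left earlier. Section 7.5.1, on deaths, says "this information will be collected in the End of Treatment or Survival Information CRF page".

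Protocol 10.5.1 words the OS rule differently again: patients alive at 16 weeks are censored at their last assessment.

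**Duration of stable disease.** SAP 1.5.1 applies this to patients whose best overall response is CR, PR or SD, and runs it from start of treatment to progression or death from the underlying disease. The censoring rule is: "Patients not experiencing progression or death at 16 weeks were censored with the date of their last tumor assessment". PFS and TTP in the same section both add the last available tumor assessment of the follow-up phase. The SAP explains that the variable replaced duration of response and that "this was changed to reach a more valuable analysis since no patient reached a best overall response of CR or PR".

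**The concern.** Kaplan-Meier estimation needs a censoring time that does not depend on whether the patient later dies. Here it does. Take two patients who both progress at the week-8 scan and have their end-of-study visit then. One dies at week 52 and enters as an event at week 52. The other is recorded alive at week 52 on the survival page and is censored at week 8. Late deaths are kept and late survival is discarded, so OS is biased downward, and the result depends partly on how long follow-up ran.

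OS is a stated secondary objective, and OS at 12 months is an optional one (protocol section 3).

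For duration of stable disease, patients event-free at week 16 contribute no later event, however the last tumor assessment is read. TTP already shows most of those late progressions. What is lost is a usable estimate for the disease-control subset, which is what the variable was introduced to provide.

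**Working it through.** **The plan's own figures.** The only computed figures in the documents are the exact binomial design characteristics. They reproduce: arm I (n = 36, at least 11 responders) gives type I error 0.0889 and type II 0.0904; arms II and III (n = 24, at least 8) give 0.0892 and 0.1919. Neither censoring rule touches them. The documents give no OS or duration figure, so what follows is illustration under stated assumptions.

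**How many patients leave the visit schedule early.** If the design's 20% and 40% are read as 16-week progression-free shares, 60–80% leave by week 16: 36 × 0.6 = 21.6 to 36 × 0.8 = 28.8 in a 36-patient arm, and 24 × 0.6 = 14.4 to 24 × 0.8 = 19.2 in a 24-patient arm.

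**OS simulation** (200,000 patients per cell).
- True OS median 40.1 weeks, the figure protocol 1.4 quotes for another mTOR inhibitor (assumed to apply here).
- Exponential PFS with median 8, 10 or 16 weeks; 10% of PFS events are deaths (assumed).
- Post-progression hazard set so that the OS median is 40.1 weeks.
- Progression is found at the next scan (weeks 8, 16, 28, 40 and so on, protocol 7.4), which is the last visit.
- All deaths before cut-off are captured.
- SAP rule: deaths at death date, everyone else at last visit. Corrected rule: everyone else at cut-off, known alive.

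Each cell gives the results for PFS medians of 8 / 10 / 16 weeks. The cut-off is either 52 weeks for every patient, or the stated minimum follow-up plus 52 weeks of accrual.

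| Cut-off (weeks) | OS median, SAP rule (weeks) | OS at 52 weeks, SAP rule | Alive at cut-off |
|---|---|---|---|
| Fixed 52 | 30.2 / 32.0 / 35.9 | 6.0 / 10.8 / 23.6% | 39 / 38 / 37% |
| 52 + 52 | 33.6 / 35.2 / 38.1 | 24.6 / 26.6 / 32.0% | 23 / 22 / 19% |
| 104 + 52 | 37.8 / 38.6 / 39.8 | 35.2 / 35.5 / 36.2% | 8 / 6 / 4% |
| 156 + 52 | 39.3 / 39.7 / 40.1 | 37.7 / 37.5 / 36.7% | 3 / 2 / 1% |

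The corrected rule gives 40.1 weeks in every cell and OS at 52 weeks of about 39 / 38 / 37%. The bias fades as fewer patients remain alive to be wrongly censored.

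Sensitivity of the SAP-rule median, in the same row order:
- Last contact 4 weeks after the progression visit: 31.6–36.5, 34.5–38.4, 38.1–39.8, 39.4–40.1 weeks.
- 30% of PFS events are deaths: 26.5–34.5, 29.5–36.7, 34.1–39.1, 36.7–39.8 weeks.

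A second model took progression and death hazards as independent, 16-week PFS of 20% or 40%, and uniform 52-week accrual. With cut-offs 26, 52 and 104 weeks after last entry, the SAP rule gave medians of 27.5–30.6, 31.3–34.0 and 36.3–37.5 weeks against 40.1. OS at 52 weeks was 12–20%, 23–29% and 35–37% against 40.7%.

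**Duration of stable disease.** Assume exponential PFS and take the subset as patients event-free at week 8. The share still event-free at week 16 is S(16)/S(8). The true subset median is 8 + ln 2/h, with h the weekly hazard.

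| Scenario | S(16)/S(8) | True median (weeks) | Scan at which it is seen |
|---|---|---|---|
| S(8) = 0.20 | 0.20 | 11.4 | 16 |
| S(8) = 0.40 | 0.40 | 14.1 | 16 |
| S(16) = 0.20 | 0.20/0.447 = 0.447 | 14.9 | 16 |
| S(16) = 0.40 | 0.40/0.632 = 0.632 | 20.1 | 28 |

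So 20–63% of the subset is event-free at week 16, and none of their later events counts. In the last scenario the SAP rule leaves the median unreached, whereas the TTP rule places it at the week-28 scan. In the other three it falls at week 16 either way.

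**The case against.** **The reading.** Table 7-1 places survival information in the End of FUP column, so a survival entry might count as the last available follow-up visit. On that reading known-alive time is kept and the asymmetry goes. This is possible, but the SAP does not say it, and its wording equates contact with visits. For a core-phase analysis it names Visit 6, which a patient who progressed earlier may never have had. Whether later deaths enter a core-phase analysis is also unstated.

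**The capture assumption.** The simulation has every late death recorded and every survivor known alive to cut-off, so recovery of 40.1 weeks is close to built in. With 75% of late deaths captured, the SAP-rule median is 38.7–42.1 weeks (104 + 52) and 40.2–42.3 (156 + 52). With 50% it is 40.0–45.3 and 41.4–45.6. The net direction can therefore reverse. This stands as a limit on the size quoted. Missing deaths are, however, a separate problem that pushes OS upward. They do not justify discarding known survival, and the fix here does not repair them.

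**The cut-off.** No passage states a 52-week cut-off, and arm III enrolment alone ran 46 months (protocol section 10). With long follow-up the shift is 0–2 weeks. The sampling error of the median is far larger: with λ = ln 2/40.1 = 0.0173, the standard error is about (0.5/√n)/(0.5λ), or 9.6 weeks at n = 36 and 11.8 at n = 24, before censoring. This stands. On the other side, both documents plan to analyse each arm once its patient number is reached, which does not guarantee mature survival data.

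**Weight.** Both endpoints are descriptive, OS at 12 months is optional, and TTP covers most of what duration of stable disease loses. All of this is true. It keeps the point below anything that affects the trial's conclusion, but it does not make the wording right.

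**Conclusion.** The concern holds. Followed as written, the OS rule counts deaths after the last visit and discards equally long known survival. The rule for duration of stable disease drops every event after week 16, although TTP in the same section does not.

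If the true OS median is 40.1 weeks and late deaths are fully captured, the main model understates the median by about 4–10 weeks at a fixed 52-week cut-off (40.1 − 35.9 = 4.2; 40.1 − 30.2 = 9.9). At 156 + 52 weeks the understatement is at most 0.8 weeks (40.1 − 39.3). The actual cut-offs are not in the documents, so the realised effect could lie anywhere in that range, including near zero, and incomplete death capture could offset or reverse it. For duration of stable disease, the median changes in one of four scenarios.

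This should be corrected, with medium confidence about its practical size. The primary decision rule, SAP PFS and SAP TTP are not affected.

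**What to change.** In SAP 1.5.1:
- **OS:** count every recorded death. Censor all other patients at the latest date known alive from any source, naming the survival information page explicitly. State the data cut-off.
- **Duration of stable disease:** use the TTP censoring rule, that is, the last adequate tumor assessment including the follow-up phase.
- Leave PFS and TTP as they are.

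Align the OS wording in protocol 10.5.1. A protocol change needs a written amendment with ethics approval (protocol Appendix 1). If that is not wanted, the departure can be recorded in the SAP's existing list of changes from the planned analysis.

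The cost is a few sentences and a rerun of the Kaplan-Meier analyses on survival-page and follow-up scan data that the protocol already collects. One point to check first: the fields of the survival page are not shown, so confirm that it holds a last-known-alive date for patients without a recorded death.
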